9.2 Rationale for Study Design

The primary efficacy measures (changes in sweat chloride, respiratory symptoms, and spirometry) are expected to change in the short term (i.e. 2-4 weeks) as shown in clinical trials, but measurement through the duration of the study will demonstrate persistence of effect with chronic therapy. The other key assessment will be the change in sputum culture results, especially related to mycobacteria. It is expected that these changes will take more time to be realized, accounting for the planned 6 months of therapy and monitoring.

As this is an n-of-2 study, there is no value to a blinded aspect for the study. Treatment will be open-label and clinical outcomes will be assessed by the individuals.

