8 STUDY ENDPOINTS

- The primary measures of efficacy will include spirometry and sweat chloride compared to baseline.
- Secondary measures of efficacy will include change in weight (BMI), respiratory symptoms (CRISS), and sputum microbiology with particular interest in mycobacterial cultures, including semi-quantitative smear and culture results.

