9 STUDY DESIGN

9.1 Overview of Study Design

This postmarketing N of 2 study is designed to evaluate the efficacy and safety of open-label ivacaftor treatment in two sisters with cystic fibrosis and pancreatic sufficiency. They have a splicing mutation that is predicted to respond favorably to ivacaftor therapy. In addition to measurement of usual clinical outcomes (i.e. lung function, nutritional status), there is great interest on the impact on nontuberculous mycobacteria (NTM) airways infection.

Subjects will undergo sputum cultures at baseline and monthly during treatment, initially in the absence of anti-NTM therapy but with the intent to treat with antibiotics if there is persistence of the infection in cultures. Other clinical outcomes will include changes in sweat chloride, lung function, respiratory symptoms (CRISS), and weight. Safety measures will include periodic assessment of liver enzymes. All serious and non-serious adverse events will be collected

9.1.1 Day 1

The investigator will obtain informed consent from the subjects (Note: they have already expressed interest in participation prior to protocol development but are aware of planned study procedures). Subjects will have blood drawn for genetic testing and undergo a physical examination, including height and weight, and measurement of baseline measures for efficacy and safety (i.e. sweat test, spirometry, respiratory symptoms (CRISS), sputum cultures for bacteria and mycobacteria, and liver enzyme testing). The subjects will commence dosing of ivacaftor on this day.

9.1.2 Months 1, 2, 3, 4, 5, and 6

Patients will be evaluated for any changes in health or medications. They will undergo physical examination, including height and weight. They will undergo measurement of efficacy outcomes (sweat test, spirometry, CRISS, sputum cultures) and safety (liver enzyme tests) as per the Study Assessment Schedule (Table 3-1).

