12.1 Sample Size and Power

This study is based upon the call for n-of-1 trials in clinical medicine; that is, single subject clinical trials that consider an individual patient as the sole unit of observation in a study investigating eth efficacy of an intervention (Lillie et al 2011), which is the heart of individualized medicine. As the patients of interest are sisters with the same mutation and similar clinical issues, this will be an n-of-2 trial. No power analysis is necessary.

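### Section 9.2 dismisses all blinding because there are only two subjects, but small numbers do not remove expectation bias, and nothing protects CRISS or the graded sputum readings from it

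*Combined protocol and SAP*

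**What the plan says.** The rationale in Section 9.2 argues that, because only two subjects are studied, "there is no value to a blinded aspect for the study". It continues: "Treatment will be open-label and clinical outcomes will be assessed by the individuals". No other reason is offered, such as feasibility, the lack of a placebo or the objectivity of the endpoints. It is also unclear who the individuals in the second sentence are: the subjects or the study staff.

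The outcomes differ in how open they are to expectation:

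- **CRISS** is self-reported. Section 9.2 groups it with the main measures: "The primary efficacy measures (changes in sweat chloride, respiratory symptoms, and spirometry) are expected to change in the short term". Section 8 and the synopsis rank it as secondary.
- **Spirometry** depends on effort. Change in percent predicted FEV1 is the primary endpoint in the synopsis.
- **Sputum microbiology** is secondary in Section 8, "including semi-quantitative smear and culture results". The synopsis endpoint for mycobacteria is conversion to a negative culture by Week 24.
- **Sweat chloride** is a laboratory measurement.

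Section 9.1 says the genotype is expected to respond. Section 9.1.1 notes that the sisters knew of the planned procedures and that "they have already expressed interest in participation prior to protocol development". Section 12 assigns the data analysis to the investigator.

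**The concern.** The argument runs from the number of subjects to the worth of blinding, and the two are unrelated. Few subjects limit precision. They do not limit the influence of expectation on what a subject reports or how a reader grades a borderline slide. With no comparator, nothing offsets that influence.

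The wording also reaches further than treatment allocation. By rejecting any blinded aspect, it closes off small protections that are compatible with open-label treatment. Two matter here.

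- A sister who has just seen a good FEV1 and then fills in CRISS is not supplying independent evidence. Agreement between the two measures would look stronger than it is.
- A reader who knows that a smear comes from an on-treatment visit may grade a borderline slide differently, in the area of infection that the protocol singles out for attention.

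**Working it through.** **No plan figure to reproduce.** Section 12.1 states that "this will be an n-of-2 trial" and that "No power analysis is necessary". It gives no effect size, SD or error rate. What follows tests the reasoning, using assumed values where marked.

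**1. Does expectation bias depend on the number of subjects?** Assume that expectation shifts each subject's change score by b = 0.5 SD (assumed, in units of the SD of within-subject change) and that subjects are independent.

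- Bias of the mean change = (n × b)/n = b = 0.5 SD for every n.
- Standard error = 1/√n SD.

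| n | Bias (SD) | Standard error (SD) |
|---|---|---|
| 2 | 0.5 | 1/√2 = 0.71 |
| 20 | 0.5 | 1/√20 = 0.22 |
| 200 | 0.5 | 1/√200 = 0.07 |

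Only the standard error changes. Having two subjects therefore does not support the statement in Section 9.2.

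**2. What could this do to a result in which both sisters improve?** Let p be the chance that one sister's score improves when the drug has no effect. Treating the sisters as independent, P(both improve) = p².

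| p (assumed) | P(both improve) |
|---|---|
| 0.5 (no expectation effect) | 0.25 |
| 0.6 | 0.36 |
| 0.7 | 0.49 |
| 0.8 | 0.64 |

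These values illustrate the mechanism. They do not estimate the bias in this study.

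**3. How many assessments are exposed?** Table 3-1 schedules CRISS, spirometry and sputum at all 8 visits. Visits 2 to 8 give 8 − 1 = 7 post-baseline assessments of each per sister. Visit 8 (Day 210) falls after the 6 months of treatment, so 7 − 1 = 6 lie within the treatment period.

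**4. Is there protection elsewhere?**

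- Table 3-1 lists what is done at each visit but not in what order.
- Sections 9.1.1 and 9.1.2 set no rule on disclosing results before CRISS.
- Section 13.2.5 requires subject numbers on case report forms, reports and study communications. That hides identity, not visit or treatment status.
- No section provides for masked reading of sputum or for independent review.

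**The case against.** The strongest reply is that the disputed sentence is followed at once by the statement that treatment is open-label, so it most naturally defends unblinded treatment, which is a reasonable choice. That stands as far as treatment goes. It does not rescue the reason given, nor the silence on assessment order and specimen labelling.

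A second reply is that the proposed steps miss the main route of bias. This also stands. Both sisters know they are on drug, they may remember results from earlier visits, and none of the steps acts on effort during spirometry. Removing that route would take a masked comparator period, which is a different study.

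A third reply is that the endpoints limit the damage. This stands in part. The synopsis symptom endpoint is change at Week 24, a single time point, so the seven scheduled scores do not all bear on it. The synopsis mycobacterial endpoint is culture conversion, which is less open to judgement than a smear grade. Sweat chloride is little exposed, so coding those samples would add little.

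Some stronger inferences are not supported:

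- **That readers are biased.** The documents do not say the laboratory is told visit or treatment status. They only fail to prevent it.
- **That analysis by the investigator distorts the results.** Sections 12.3.1 and 12.3.3 plan descriptive summaries, full listings and a fixed change formula, which leave little for a masked analyst to protect.
- **That the sisters' early interest shows biased reporting.** It is weak evidence of that.

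**Conclusion.** The concern holds in a limited form. The reason in Section 9.2 is wrong, and the plan leaves CRISS and the semi-quantitative sputum readings without simple protection. This is a cheap improvement and not a flaw that invalidates the study.

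A reader might infer that the study ought to be blinded, or that masking would make the efficacy results free of bias. The documents support neither. Open-label treatment is acceptable with two subjects and no comparator, and expectation would still act on CRISS and on FEV1 after every step below.

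The size of the bias is unknown. The 0.5 SD shift and the values of p are assumptions, and independence between sisters is a simplification. The conclusion that bias does not shrink with n needs only a shift that is the same on average for each subject.

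**What to change.** 1. In Section 9.2, replace the sentence on blinding with the actual reason treatment is open-label.
2. Under Table 3-1, require CRISS to be completed first at every visit, before spirometry and before any result from that visit is disclosed.
3. Send sputum to the laboratory under a code that carries neither visit number nor treatment status. A new code for each specimen is preferable, since a repeated subject number would show the sequence. The site should relink each result promptly, because Section 9.1 makes antibiotic treatment depend on the cultures.
4. State who assesses the clinical outcomes.
5. List the remaining expectation bias in CRISS and in effort-dependent FEV1 as a limitation. Treat CRISS as supportive, in line with its secondary rank in Section 8 and the synopsis, and correct the grouping in Section 9.2 to match.

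**Cost.** No extra visit, test or subject is needed. The steps are not free: staff must hold the visit order and relink coded specimens without delay. The documents give no staffing or laboratory information from which to price this.

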10 SELECTION OF STUDY POPULATION

10.1 Inclusion Criteria

Subjects include two identified sisters with CF gene mutations expected to respond to ivacaftor. They fulfill the following criteria:

- Subjects are >18 years of age and able to provide informed consent.
- Subjects reside in the US and are willing to be treated with ivacaftor.
- Subjects have the splicing mutation of interest.
- Subjects are willing and able to perform requirements of the study.

10.2 Exclusion Criteria

There are no relevant exclusion criteria for this n-of-2 study.

11 ASSESSMENTS

11.1 Timing of Assessments

The timing of assessments is shown in Table 3-1.

Medical University of South Carolina

Confidential Information

11.2 Subject and Disease Characteristics

Subject and disease characteristics include the following: *CFTR* genotype, sex, race, age, weight, height, body mass index (BMI), age at CF diagnosis, and relevant medical history. Supplemental medical history may be collected from the Cystic Fibrosis Foundation (CFF) Patient Registry.

11.3 Ivacaftor Exposure

The start and stop dates of all ivacaftor treatment will be recorded; all unique dosing intervals will be recorded during the study.

11.4 Prior and Concomitant Medications

Information regarding all medications administered before study enrollment and through the last study visit will be recorded.

11.5 Safety

11.5.1 Adverse Events

All serious and non-serious adverse events will be assessed and documented.

12 STATISTICAL AND ANALYTICAL PLANS

Data analysis will be performed by the investigator.

12.1 Sample Size and Power

This study is based upon the call for n-of-1 trials in clinical medicine; that is, single subject clinical trials that consider an individual patient as the sole unit of observation in a study investigating eth efficacy of an intervention (Lillie et al 2011), which is the heart of individualized medicine. As the patients of interest are sisters with the same mutation and similar clinical issues, this will be an n-of-2 trial. No power analysis is necessary.

12.2 Analysis Sets

There is only one set of data to be analyzed, consisting of the 2 subjects enrolled in this study. They will comprise both the **Enrolled Set** and the **Safety Set**.

12.3 Statistical Analyses

This section presents a summary of the planned statistical analyses of safety. Analysis details will be provided in the Statistical Analysis Plan (SAP) for this study, which will be finalized before study database lock.

12.3.1 General Considerations

Continuous data variables (e.g., FEV₁) will be summarized using descriptive summary statistics. Categorical data (e.g., sex) will be summarized. All subject data, including those derived, will be presented in the subject data listings.

12.3.2 Background Characteristics

12.3.2.1 Subject Disposition

The number of subjects in each disposition category (e.g., enrolled; prematurely discontinued from the study; and completed the study) will be summarized.

12.3.2.2 Demographics and Baseline Characteristics

The following demographic and baseline characteristics will be captured: *CFTR* genotype, sex, race, age, weight, height, BMI, sweat chloride, spirometry, CRISS, and sputum culture results.

12.3.2.3 Prior and Concomitant Medications

Only prior and concomitant corticosteroids and ivacaftor will be collected. Medications taken during the collection period specified in Section 11.4 will be summarized by preferred term using the World Health Organization Drug Dictionary (WHO-DD) for the Safety Set as frequency tables in 2 parts:

- Prior medication: medication that started before the first dose of ivacaftor, regardless
 of when dosing of the medication ended.
- Concomitant medication: medication received at or after the first dose of ivacaftor, medication that was received before initial dosing of ivacaftor and continued after initial dosing, or medication with missing stop date.

Medications that started before the first dose of ivacaftor and continued after the first dose of ivacaftor will be summarized separately as prior medications and concomitant medications, respectively. Medications with a missing start date will be considered to have a start date before the first dose of ivacaftor.

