2 PROTOCOL SYNOPSIS

T			
Title	An Efficacy and Safety Study of Ivacaftor in Patients With Cystic Fibrosis		
	and Splicing Mutations		
Clinical Phase	N of 2 Study		
Objective	To evaluate the efficacy and safety of ivacaftor in two patients (sisters)		
	who have a splicing mutation and pancreatic sufficiency		
Endpoints	Primary		
	Absolute change in percent predicted forced expiratory volume in		
	1 second (FEV ₁) from baseline through Week 24		
	Key Secondary		
	Relative change in percent predicted FEV1 from baseline through		
	Week 24		
	Achievement of mycobacterial culture conversion (negative		
	culture) by Week 24		
	 Secondary Safety and tolerability assessments based on adverse events (AEs), 		
	clinical laboratory values (i.e., liver function tests)		
	Absolute change in sweat chloride from baseline through Week 24		
	Absolute change in respiratory symptom scores from baseline at		
	Week 24		
Study	Sisters with specific mutations		
Population			
Number of	2		
Subjects			
Study	Subjects will be treated for 6 months and followed for 7 months		
Duration			
Study Design	This postmarketing N of 2 study is designed to evaluate the efficacy and		
	safety of open-label ivacaftor treatment in two sisters with cystic fibrosis		
	and pancreatic sufficiency. They have a splicing mutation that is predicted		
	to respond favorably to ivacaftor therapy. In addition to measurement of		
	usual clinical outcomes (i.e. lung function, nutritional status), there is great		
	interest on the impact on nontuberculous mycobacteria (NTM) airways		
	infection.		
	Subjects will undergo sputum cultures at baseline and monthly during		
	treatment, initially in the absence of anti-NTM therapy but with the intent		
	to treat with antibiotics if there is persistence of the infection in cultures.		
	Other clinical outcomes will include changes in sweat chloride, lung		
	function and weight. Safety measures will include periodic assessment of		
Assessments	liver enzymes. All serious and non-serious adverse events will be collected		
Assessifients	Efficacy: spirometry, sweat chloride testing, CRISS, sputum cultures		
	(bacteria and mycobacteria), height, and weight Safety: AEs, clinical laboratory assessments (liver function tests), vital		
	signs, physical examinations, and pulse oximetry		
Statistical	Statistical analysis details will be provided in the Statistical Analysis Plan		
Analyses	(SAP), which will be finalized before the clinical data lock for the study.		

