13.3 Data Quality Assurance

The investigator will prepare and maintain adequate and accurate case histories designed to record all observations and other data pertinent to the study for each study participant. Study data for each enrolled subject will be entered into a CRF by site personnel using a secure, electronic data capture (EDC) application. Any changes to study data will be made to the CRF and documented in an audit trail, which will be maintained within the study database.

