13.4 Data Capture

It is the investigator's responsibility to ensure the accuracy, completeness, clarity, and timeliness of the data reported in the subject's CRF. Source documentation supporting the CRF data should indicate the subject's participation in the study and should document the dates and details of study procedures, adverse events, other observations, and subject status.

The investigator will retain the CRF data and corresponding audit trails that show all updates to data, with user identification, date, and time.

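### Section 12.3.2.3 limits medication collection to corticosteroids and ivacaftor, contradicting Section 11.4; if it is followed, any anti-NTM antibiotics need not reach the CRF or listings

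*Combined protocol and SAP*

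**What the plan says.** Two sections of the protocol define which medications are gathered.

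- Section 11.4, under Assessments: "Information regarding all medications administered before study enrollment and through the last study visit will be recorded".
- Section 12.3.2.3, under the statistical plans: "Only prior and concomitant corticosteroids and ivacaftor will be collected". Its next sentence begins: "Medications taken during the collection period specified in Section 11.4 will be summarized by preferred term". It then gives rules for sorting medications into prior and concomitant.

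The design makes one drug class outside the narrow list important. Under Section 9.1 and the synopsis, the subjects start without anti-NTM therapy, "with the intent to treat with antibiotics if there is persistence of the infection in cultures". The synopsis makes mycobacterial culture conversion by Week 24 a key secondary endpoint. Section 8 lists sputum microbiology as a secondary measure, with particular interest in mycobacterial cultures and including semi-quantitative smear and culture findings.

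**The concern.** One section says all medications and the other says only two kinds. Site staff building or completing the CRF could follow either and be compliant with the protocol as written. If they follow Section 12.3.2.3, an antibiotic started for persistent NTM falls outside the stated collection. A reader of the listings could then see a culture turn negative, or a smear or culture grade fall, without being able to tell whether antibiotics had already begun. In an open-label study of two subjects with no control group, dated individual records are the plan's only means of making that distinction.

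**Working it through.** The plan states no figure on this point and no arithmetic loss is claimed. The check is a comparison of texts.

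1. **Do the two rules conflict?** Section 11.4 covers all medications. Section 12.3.2.3 covers corticosteroids and ivacaftor only. Anti-NTM antibiotics are inside the first scope and outside the second, so the conflict is direct.

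2. **Does the cross-reference resolve it?** No. Section 12.3.2.3 cites Section 11.4 for the collection period, not for the drug classes.

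3. **Does other text settle the scope?** Table 3-1 has a concomitant-medication row marked at all 8 visits, and Section 9.1.2 has medication changes reviewed at the monthly visits. Both fit Section 11.4, but neither states a drug-class scope, so neither overrides the word *only*. Section 12.3 leaves analysis details to a SAP to be finalized before database lock. That could come after data entry, and it does not rank the two rules.

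4. **Can antibiotics overlap the endpoint window?** Week 24 is 24 × 7 = 168 days. Table 3-1 schedules post-baseline sputum cultures at Days 30, 60, 90, 120 and 150, all before Day 168. Persistence could therefore be seen, and antibiotics started, before the endpoint is reached. The documents do not say when or whether this will happen.

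5. **Would the antibiotics be captured elsewhere?**
   - Section 13.1.3 asks for treatment given for an adverse event, without asking for drug dates. Under Section 13.1.1 a previous condition becomes an adverse event only if it worsens in severity or frequency, so NTM that merely persists need not qualify.
   - Section 13.3 requires case histories "designed to record all observations and other data pertinent to the study" and entry of study data in the CRF. It does not say that antibiotics count as study data when another section excludes them.
   - Section 13.4 says that source documents "should document the dates and details of study procedures, adverse events, other observations, and subject status". Medications are not named.
   - Section 12.3.1 puts all subject data in the listings, but only what has been collected can appear there.

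6. **Which results are touched?** Both mycobacterial measures. Conversion by Week 24 may occur before or after antibiotics start. A culture that is still positive but shows a lower burden is also affected, because Section 8 makes the semi-quantitative findings a secondary measure.

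**The case against.** The strongest reply is that the documents lean towards Section 11.4. It sits in Assessments, where one expects to find what is gathered, whereas Section 12.3 describes itself as a summary of the planned safety analyses. Table 3-1 and Section 9.1.2 fit Section 11.4, so a single sentence is the outlier. Anti-NTM therapy is named in the design and is hard to call irrelevant to the case histories. There are two subjects at one site, and the investigator maintains the records, analyses the data and writes the report. An antibiotic start that nobody notices is unlikely.

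Most of this stands, and it makes the consequence conditional. It does not remove the conflict: no text ranks the rules, and the backstops do not ensure that antibiotic names and dates reach the CRF and listings. One could read *recorded* as source notes and *collected* as CRF data, but the documents draw no such distinction, and on that reading antibiotics would still be missing from the CRF. The report also goes to the manufacturer and the FDA (Section 13.5.2), so the investigator's own knowledge of the subjects is not a substitute.

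Three further readings are tempting and should not be adopted.

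- A reader might infer that the antibiotic dates would be lost for good. Source records may hold them.
- A reader might infer that only negative cultures are affected. The semi-quantitative measure in Section 8 rules that out, and an early positive culture does not establish non-conversion by Week 24.
- A reader might infer that full antibiotic dates would let a conversion be credited to ivacaftor. They would only place the result before or after antibiotic start; the uncontrolled, open-label design leaves attribution open.

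**Conclusion.** The contradiction between Sections 11.4 and 12.3.2.3 is real and should be corrected; confidence in that is high. The consequence rests on two assumptions: that Section 12.3.2.3 is the rule followed, and that anti-NTM antibiotics are started. If both hold, mycobacterial results could not be classified from the study data as before or after antibiotic start. That affects an endpoint the synopsis ranks as key secondary and Section 8 ranks as secondary, together with the semi-quantitative findings. If Section 11.4 is followed, only contradictory wording remains. The documents give no basis for counting the results affected, so no numerical size is stated.

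**What to change.** Delete the sentence in Section 12.3.2.3 that restricts collection to corticosteroids and ivacaftor, and reconcile the section with Section 11.4. Suggested replacement: *All prior and concomitant medications within the scope of Section 11.4, including any anti-NTM antibiotics, will be entered in the CRF and listed by subject with start and stop dates.*

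The rest of Section 12.3.2.3 can stay. Its sorting rules already depend on dates, as in "Medications with a missing start date will be considered to have a start date before the first dose of ivacaftor", so no new type of data is needed. Make the change before data entry rather than leaving it to the SAP.

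Showing antibiotic dates beside the mycobacterial results in one listing is an optional, low-cost addition, not part of curing the contradiction.

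The cost is a one-sentence amendment and negligible extra data entry for two subjects, at 8 visits where concomitant medications are already scheduled. The change concerns data collection only and implies nothing about when or how antibiotics are given.
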